### 17.3 Myocardial infarction

Diagnosed in the following situations(30)

- Increase and/or fall in specific biomarkers (mainly troponin) with at least 1 value higher than the 99 percentile of upper reference threshold and

Evidence for myocardial ischemia with at least one of the following:

- Symptoms of ischemia ( chest pain, dyspnoea, acute heart failure, arrhythmia)
- ECG changes indicative of acute ischemia (new ST-T changes or new left side bundle branch block)
- Development of pathological Q-waves on ECG
- Radiological diagnostic evidence of new loss of viable myocardium or new regional dyskinesia.
- Revascularisation by PCI or CABG.

## 17.4 Stroke

Defined as an acute neurological event with focal neurologic deficits and duration beyond 24 hours (31), verified by CT/MR-scan. Strokes will be stratified according to type as ischemic, hemorrhagic or unknown.

In case of progression of formerly known neurological symptoms, the progression must be present for more than 1 week or 24 hours if accompanied by new relevant CT or MR findings.

### **Cardiovascular death**

Death of vascular causes include cardiovascular, cerebrovascular and death of other vascular causes or death with no clear documentation of non-vascular cause. Ex:

Vascular death: Sudden death, MI, unstable angina pectoris, other CAD, stroke, arterial embolism, pulmonary embolism, dissecting aorta, heart insufficiency, cardiac arrhythmia, or death from bleeding (non-trauma related)

Non-vascular death: Respiratory failure, pneumonia, cancer, trauma, suicide or other defined cause (i.e. liver or renal failure)

Death of unknown /uncertain causes will be categorized as vascular death.

### **TCI**

Definition is as for stroke, but are temporary and gone <24 hours.

## 17.5 Other thromboembolic events

Need to be defined by a relevant specialist.

## 18. Appendix 4

Date of surgery

Social security number

Joint (knee/hip)

Height: \_\_\_\_\_ cm

Weight: \_\_\_\_\_ kg

Hemoglobin level \_\_\_\_\_ mmol/l

(Taken no more than 1 week previously)

Patients' blood type?

Living conditions (alone, with spouse/others, in institution (nursing home etc.))

Smoking (yes/no)

Alcohol >2 units a day (yes/no)

Do you use walking aids prior to admission?

Are you feeling well rested in the morning?

Do you snore loudly?

Do you use compressive stockings regularly?

Do you receive treatment for high cholesterol (yes/no)

Do you receive treatment for high blood pressure (yes/no)

Do you have Type 1 diabetes (yes/no)

Do you have Type 2 diabetes (yes/no)

Have you had a previous cerebral attack?

Have you had a previous venous thromboembolic event?

Do you receive medication for any type of heart disease?

Do you receive medication for any type of pulmonary disease?

Do you receive medication for any type of psychiatric disease?

Do you have a family member who has had a deep venous thrombosis or pulmonary embolus?

Do you have a contraindication for antithrombotic medication?

Do you use antithrombotic medication regularly (marevan, acetyl salicylic acid etc)?

## 19. Protocol editing and changes after study initiation

- 1) **Project leader and coordinating investigator:** Changed from [name] to [name]
- 2) **Other investigators:** The following investigators have been removed as the study was not initiated at their institutions: [name] MD, Århus Universitety Hospital, THG Århus, [name] MD, Regionshospitalet Silkeborg.  
The following investigators have been edited: [name] MD, Gentofte Hospital Gentofte.  
The following investigators have been added: [name] MD, Sydvestjysk Sygehus Grindsted/Esbjerg
- 3) **Statistician:** [name] is no longer responsible for statistics. [name] has been added and additional assistance will be acquired as needed.
- 4) **Study sites:** The following study sites have not participated: Regionshospitalet Silkeborg, Hørsholm Hospital (due to closure). The following study sites have been added: Sydvestjysk Hospital Grindsted/Esbjerg April 2010, Gentofte Hospital, November 2012.
- 5) **Background:** Hørsholm Hospital has been mentioned as having used short-treatment prophylaxis as standard of care. This is a mistake and should be omitted.
- 6) **2.1 Design:** Due to a large number of available patients, it has been decided to expand the study size. The intention is now to include 5000 PRIMARY operations in addition to a number of revisions and uni-KA. 3.
- 7) **3. Patient selection:** Changes according to 4) **Study sites.**
- 8) **3.3 Discharge criteria:** Thrombosis prophylaxis in patients with LOS >5 days: DOS guidelines are not 7 days, but 5-10 days in TKA and 7-35 days after THA.
- 9) **4. Statistics:** The exact number of patients when using a Two-tailed one sample difference from constant test with the in the protocol mentioned specifications is 2838. Using the same test, 2076 patients will be needed to detect a 1% increase in frequency of symptomatic VTE, using  $\alpha$ : 0.05,  $\beta$ : 82 and a baseline risk of 1% with 35 days of treatment with LMWH.
- 10) **7. Duration of study:** As the database of this study forms the core of several independent studies on co-morbidity, duration of this study has been extended, and database registration is expected to last until ultimo 2016
- 11) **9. Data collection:** Collection of data has been changed from depending on ICD-10 diagnostic codes for vascular events only to include ALL readmissions in 90 days. These will be investigated using discharge papers and complete medical charts in order to increase quality of data. In addition further details on regular anti-coagulative therapy 6 months prior to surgery and 3 months after surgery be collected through a newly established cooperation with the Danish National Database of Reimbursed Prescriptions, in order to further improve data quality.
- 12) **10. Authors:** [name] is now primary author, [name] will figure as secondary author and [name] as senior author. The remaining investigators are co-authors in a random order when patients from their study sites are included in the specific studies.
- 13) **11.1 Steering committee:** The following persons are not part of the steering committee: [name], [name], [name], [name].
- 14) **11.2 Clinical event Committee:** Consists of [name] and [name].
- 15) **12.1 Ethic Committee:** The study ended up being considered as a quality-control study on a standard of care. The Scientific Ethics Committee decided that the study needed no approval.
- 16) **Appendix 1:** The local prophylaxis guidelines of the following departments are not relevant: Hørsholm and Silkeborg. Guidelines for the added departments are: Gentofte Hospital: X10a inhibitor (Xarelto) 10 mg x 1 in both THA/TKA until discharge. Sydvestjysk Sygehus Grindsted: LMWH (Arixtra) 2.5mg x 1 for 7 days. Treatment has been changed after study initiation in the

following departments: Hvidovre Hospital: X10a inhibitor (Xarelto) 10 mg to discharge THA/TKA.  
Viborg Hospital: LMWH (Fragmin) 5000 ie x 1 for 10 days.

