## 4. Statistics

A pre-study power-calculation showed that at least 3000 patients were needed (power( $\beta$ ) 82 % with a significance level ( $\alpha$ ) of 0,05) with expected event-rates of 3% (22-25) and a maximum event rate of 4 %. We expect to include about 5000 patients which would increase power and the statistic possibility of identifying risk-factors (preoperative variables). In addition isolated analysis on the primary procedures will be performed.

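### The 2076 patients given for symptomatic VTE do not follow from the stated 1% baseline and 1-point increase; the same test gives 1143

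*Combined protocol and SAP*

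**What the plan says.** Section 4 (Statistics) sizes the study on an overall event rate, "with expected event-rates of 3% (22-25) and a maximum event rate of 4" per cent, with alpha 0.05 and 82% power, and rounds the requirement to at least 3000 patients.

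Section 19, item 9 replaces that round number. It says the exact number from a "Two-tailed one sample difference from constant test with the in the protocol mentioned specifications is 2838". It then adds a second calculation that appears nowhere else: by the same test, "2076 patients will be needed to detect a 1% increase in frequency of symptomatic VTE", with alpha 0.05, 82% (labelled beta, though it is the power) and "a baseline risk of 1% with 35 days of treatment with LMWH".

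Item 6 of the same section sets the enrolment target: "The intention is now to include 5000 PRIMARY operations in addition to a number of revisions and uni-KA".

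**The concern.** Item 9 supplies every input to the second calculation: the test, alpha, the power, the baseline and the size and direction of the change. The figure should therefore be reproducible. A 1-point difference between 1% and 2% involves much less binomial variance than a 1-point difference between 3% and 4%, so the number needed should fall well below half of 2838. Instead, 2076 is nearly three quarters of it (2076 / 2838 = 0.73).

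The hypothesis in section 1.2 concerns symptomatic thromboembolic events, and item 9 holds the only sample size for symptomatic VTE. If that figure belongs to other rates, the stated inputs or the stated N is wrong, and the reader cannot tell which. Copied into a report, it would be a power statement that nobody could reproduce.

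**Working it through.** **Inputs**

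- Test: two-tailed, one-sample, against a constant (section 19, item 9).
- Alpha 0.05, power 82% (section 4 and item 9).
- Main calculation: constant 4%, true rate 3% (section 4).
- VTE calculation: constant 1%, true rate 1% + 1% = 2% (item 9).
- No dropout allowance is given.

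**Method.** For N patients, X ~ Binomial(N, p). With constant p0, reject if X ≤ L or X ≥ U, where L is the largest count with P(X ≤ L | p0) ≤ 0.025 and U is the smallest with P(X ≥ U | p0) ≤ 0.025. Power is P(X ≤ L | p1) + P(X ≥ U | p1). Exact power moves in a sawtooth as N grows, so two figures are given: the first N that reaches 82%, and the N from which power stays at or above 82%.

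**Step 1: reproduce 2838 (constant 4%, true 3%)**

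- N = 2837: L = 92, U = 135, power 79.4%.
- N = 2838: L = 93, U = 135, power 82.2%.

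The first N is 2838, exactly as item 9 states. Power is stable only from 3003, so item 9 reports the first N.

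**Step 2: the same test on the VTE inputs (constant 1%, true 2%)**

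- N = 1142: L = 4, U = 19, power 81.94%.
- N = 1143: L = 4, U = 19, power 82.05%.

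The first N is 1143, and power is stable from 1308. With the roles reversed (constant 2%, true 1%), the first N is 1233, stable from 1418. Neither is near 2076.

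**Step 3: what 2076 delivers for the stated rates**

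- Constant 1%, N = 2076: L = 11, U = 31.
- Power at a true rate of 2%: 96.3%.
- Power at 1.70% is 78.9% and at 1.75% is 83.5%, so 82% is reached at about 1.73%.

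**Step 4: could another formula explain it?** The normal approximation is

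N = [(1.960·√(p0(1−p0)) + 0.915·√(p1(1−p1))) / (p1 − p0)]²

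For 1% versus 2%, this is [(1.960 × 0.0995 + 0.915 × 0.1400) / 0.01]² ≈ 1045. Other variants for the same rates:

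| Variant | N |
|---|---|
| Exact, one-sided | 921 |
| Normal, two-sided, continuity-corrected | 1143 |
| Arcsine, two-sided | 1187 |
| Normal, rates reversed | 1336 |
| Normal, alternative variance only, continuity-corrected (largest one-sample variant) | 1719 |
| Two-sample, one-sided, per arm, without / with continuity correction | 1936 / 2132 |
| Two-sample, two-sided, per arm, without / with continuity correction | 2442 / 2638 |

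No one-sample variant reaches 2076. The nearest two-sample value, 2132, misses it by 2.7%, is not the test that item 9 names, and would need 2 × 2132 = 4264 patients in total.

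A relative reading (1.00% to 1.01%) does not help either: (1.960 + 0.915)² × 0.0099 / 0.0001² ≈ 8.2 million.

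**Step 5: which rates do give 2076?** Constant 3%, true 2%:

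- N = 2075: L = 46, U = 79, power 78.6%.
- N = 2076: L = 47, U = 79, power 82.7%.

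The first N is exactly 2076. In a search over ordered pairs of rates from 0.5% to 6% in 0.1-point steps, with differences up to 2 points, no other pair gave that value.

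**Step 6: effect on the planned study**

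| N | Power, constant 1%, true 2% | Power, constant 3%, true 2% |
|---|---|---|
| 1143 | 82.0% | 48.3% |
| 2076 | 96.3% | 82.7% |
| 5000 | above 99.9% | 99.5% |

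**The case against.** The strongest objection is that nothing depends on this number. Section 4 and the interim analyses in section 8 work with the overall event rate against 4%, and item 6 attributes the larger enrolment to patient availability, not to 2076. On the inputs as written, 2076 is more than enough. This stands, and it limits the point to a minor one.

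It can also be said that item 9 does state a baseline, a change and a direction. That is true. The uncertainty is whether those inputs or the N is wrong.

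The document does not name the exact binomial test; it is inferred because it returns 2838. The inference is strong, and the mismatch survives every one-sample alternative tried. The 3%-versus-2% explanation is weaker: no passage gives either figure as a VTE rate, and the 3% in section 4 is the expected overall event rate. It remains a probable cause only, and the mismatch does not depend on it.

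The size of the error depends on convention: 2076 is about 1.8 times 1143 (first N) but about 1.6 times 1308 (stable N).

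Finally, section 19 is a list of changes. However, the contradiction lies within item 9, between its N and its own inputs. It is not a difference between a log and the current text.

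**Conclusion.** The point holds, as a minor documentation error. Under the test that reproduces 2838 exactly, detecting a rise from 1% to 2% needs 1143 patients on the convention item 9 follows, or 1308 if 82% power must hold for all larger samples. The stated 2076 has 96.3% power for that rise, and it is the exact answer for 2% against a constant of 3%.

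This rests on reading the 1% increase as one percentage point, the 82 as power, and the test as an exact binomial with alpha split equally between the tails. As worded, the error is conservative. With 5000 primary operations, power is at least 99.5% for either pair of rates, so neither enrolment nor the planned analyses are affected.

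**What to change.** First confirm from the calculation record which rates were entered. Then correct item 9 so that the constant, the assumed true rate and the direction stand next to the N.

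- If a rise from 1% to 2% was meant: restate N as 1143, noting that 82% power is stable only from 1308. Alternatively, keep 2076 and state that it gives about 96% power.
- If 2% against a constant of 3% was meant: keep 2076 and correct the baseline and the direction.

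The rates must be settled before N is changed, because 1143 patients would give only 48% power for 3% versus 2%. Label the 82 as power in the same edit. The cost is one corrected line, with no change to enrolment or analysis.

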## **Background:**

Surgery is recognized as being related to the development of thrombosis, especially after major orthopedic surgery (1;2). These complications are defined as venous thromboembolic events (VTE), including deep venous thrombosis (DVT) and pulmonary embolism (PE).

Pharmacological prophylaxis reduces the risk of thrombosis and recommendations (grade 1a) from the American College of Chest Physicians (ACCP) are one of three following anticoagulantia:

1: Low molecular weight heparin (LMWH)

2: Faktor Xa-inhibitors

3: Vitamin-K-antagonists

Recommended duration of thrombosis prophylaxis is 10 days after total knee arthroplasty (TKA) and 35 days after total hip arthroplasty (THA) (3).

In the United States of America most surgeons follow ACCP guidelines. Studies have shown that about 90 % of surgeons adhere to guidelines, however, many use additional prophylaxis such as compressive stockings(4). More recent investigations find a lower compliance amongst surgeons world wide of about 50% (5). There are disagreements about the validity of the before mentioned guidelines due to the many exclusion and inclusion criteria in the analyzed studies and due to the fact that it is the thoracic surgeons who dictate the orthopedic surgeons guidelines(6), therefore the American Academy of Orthopedic Surgeons (AAOS) has developed their own guidelines. The main difference between ACCP and AAOS guidelines is the use of compressive stocking and acetylsalicylic acid as only prophylaxis in patients at risk of bleeding and a general disagreement on the relationship of DVT and PE(7).

In Denmark, the Danish Society of Orthopedic Surgeons (DSOS) has their own guidelines of 7 days of postoperative thrombosis prophylaxis which illustrates the controversies in this area.

The few studies who do not comply with ACCP guidelines, using acetylsalicylic acid (and early mobilization) as only prophylaxis show very low frequencies of vascular events (8-11), raising doubts about the best choice of treatment, especially considering increased mortality with LMWH compared to acetylsalicylic acid(12).

Preliminary uncontrolled studies in TKA have shown that early mobilization (<24 hours after surgery) reduces risk of postoperative VTE in patients treated with LMWH(13), and as frequency of DVT following TKA is decreasing over time using warfarin (VKA) as prophylaxis(14), interest in postoperative mobilization is increasing.

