The trend towards enhanced recovery protocols (fast-track surgery) where optimized pain treatment, early mobilization (<24 hours), preoperative patient information etc. aims to decrease length of hospital stay. Data on THA and TKA patients from Hvidovre Hospital proves that 92 % of patients were discharged within 5 days and 41 % within 3days(15).

An un-published preliminary study from Hvidovre Hospital in about 2000 patients shows very low frequency of symptomatic VTE in 90-days follow-up, with mortality of 0.15%, DVT/PE/death in TKA of 0.66%

and 0.52% in THA when using a fast-track setup (16). This is lower than comparable literature with thrombosis prophylaxis for 35 days postoperatively.

A group of experts has suggested that pharmacological thrombosis prophylaxis in patients with early mobilization is non-obligatory, this would result in decreased side-effects such as bleedings, less inconvenience in the patients and economical advantages(17). This has resulted in short prophylaxis treatment being standard of care in several departments in Denmark (i.e. Hørsholm, Hvidovre and Farsø hospitals).

No previous study has been published with a detailed description on the risk of vascular events, including arterial complications, using short-treatment thrombosis prophylaxis in a fast-track setup after THA/TKA or commented on identification of risk factors(2;18;19).

It must be mentioned that Asian patients (Korea, China etc.) do not have a tradition for thrombosis prophylaxis after THA due to the low frequencies of VTE without prophylaxis. In this context, differences in genetics and dietary habits etc. must be considered (20;21).

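### Judging symptomatic VTE against item 9's fixed 1% would make any 'no increase versus 35 days of LMWH' conclusion depend on an unsourced figure whose uncertainty is ignored

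*Combined protocol and SAP*

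**What the plan says.** Section 1.2 states a comparative hypothesis: symptomatic thromboembolic events are not more frequent with short prophylaxis in a fast-track setup. Section 2.1 describes a single cohort followed for 90 days, with no concurrent group on 35 days of prophylaxis.

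Section 19, item 9 holds the only quantified VTE comparison. It names a "Two-tailed one sample difference from constant test" and states that "2076 patients will be needed" "to detect a 1% increase in frequency of symptomatic VTE", with alpha 0.05, power 82% (labelled beta) and "a baseline risk of 1% with 35 days of treatment with LMWH". No citation, event count, patient count, interval or follow-up window accompanies the 1%. Section 19, item 6 sets the cohort at 5000 primary operations.

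The only decision analysis written out is in Section 8: exact CIs for the complication risk, set against 4%. Section 4 calls that 4% a maximum event rate. The 1% in item 9 is instead described as the risk in other patients on another regimen.

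The Background gives DVT/PE/death of 0.66% (TKA) and 0.52% (THA) in about 2000 local fast-track patients and comments: "This is lower than comparable literature with thrombosis prophylaxis for 35 days postoperatively". It gives no rate for that literature.

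**The concern.** A one-sample test treats its reference value as known exactly. That is right for a chosen ceiling. It is not right for a risk estimated in other patients, which has sampling error and may not match this cohort's era, case mix or 90-day window. The test counts only the cohort's own error: with 5000 patients at 1%, the standard error is √(0.01 × 0.99 / 5000) = 0.14 percentage points. Any error in the 1% is then credited to, or charged against, short prophylaxis.

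The stakes run both ways. If the 1% is too low, an unchanged risk looks like harm. If it is too high, a real increase is hidden, and a false 'no increase' would be used to support shorter prophylaxis. Enlarging the cohort shrinks its own error but not the baseline's.

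**Working it through.** **Inputs.** Constant 1%, alternative 2%, two-sided alpha 0.05, power 82%, n = 2076 (Section 19, item 9). Cohort 5000 (Section 19, item 6). Expected 3% against a maximum of 4% (Section 4). The precision of the 1% is not given, so step 4 rests on assumed source sizes.

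**Step 1: the plan's own figures.** Exact two-sided one-sample binomial test, alpha/2 per tail, smallest n reaching 82% power.
- Constant 4%, true 3%: n = 2838, power 82.2%. This matches item 9 and identifies the method.
- Constant 1%, true 2%: n = 1143, power 82.0%. Item 9's 2076 does not follow from its stated inputs. It is the first n that works for constant 3%, true 2% (82.7% at 2076; 78.6% at 2075). At n = 2076 the power for 1% versus 2% is 96.3%.

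This mismatch is a separate matter that should be corrected. Below, 2076 serves only as the smaller of two sample sizes.

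**Step 2: the rule against a literal 1%.** The limits are the smallest h with P(X ≥ h | n, 0.01) ≤ 0.025 and the largest l with P(X ≤ l | n, 0.01) ≤ 0.025.

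| n | 'lower' | 'increase' | exact alpha |
|---|---|---|---|
| 2076 | ≤ 11 | ≥ 31 (1.49%) | 1.4% + 2.1% = 3.5% |
| 5000 | ≤ 36 | ≥ 65 (1.30%) | 2.3% + 2.3% = 4.6% |

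**Step 3: the same rule when the true 35-day risk is not 1%.** No source size has to be assumed here. Short treatment changes nothing, so the cohort's risk equals the true 35-day risk p. The false 'increase' rate is P(X ≥ h | n, p).

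| true 35-day risk | n = 2076 | n = 5000 |
|---|---|---|
| 1.1% | 6% | 10% |
| 1.2% | 13% | 27% |
| 1.3% | 24% | 52% |

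In the other direction, let the true 35-day risk be 0.7% and the risk with short treatment 1.0%. Then 'increase' is declared with probability P(X ≥ h | n, 0.01), which is 2.1% at 2076 and 2.3% at 5000. If short treatment has no effect at 0.7%, 'lower' is declared 61% of the time at 5000.

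A borderline result shows the dependence directly: 65 events in 5000 gives two-sided p = 0.046 against 1.0% but p = 0.20 against 1.1%.

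**Step 4: sampling error in the 1% (source sizes assumed).** Suppose the 1% was estimated from m patients. Draw the true risk from Beta(0.01m + 0.5, 0.99m + 0.5), give the cohort the same risk, and average the rejection probabilities.

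| m | false 'increase', n = 2076 | false 'increase', n = 5000 | false 'lower', n = 5000 |
|---|---|---|---|
| 2000 | 8.8% | 15.8% | 12.8% |
| 4000 | 5.5% | 10.0% | 8.3% |
| 10,000 | 3.4% | 5.5% | 4.8% |
| 50,000 | 2.3% | 2.9% | 2.8% |

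The intended rate per tail is about 2.5%.

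**The case against.** Several points on the other side stand.

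- **Item 9 is a sample-size statement.** A fixed null value is normal there, and nowhere do the documents say that the VTE result will be tested against 1%. The title page calls the study descriptive. The concern is therefore conditional on how the result is used. It is not empty: item 9 names the test, the hypothesis is comparative, and no other VTE analysis is given.
- **Alpha is not lost at the null value.** A reader might infer that the stated 0.05 is simply wrong. Step 2 shows that it holds against the literal 1%. What fails is the wider claim about the risk with 35 days of LMWH.
- **The inflation from sampling error cannot be derived from the documents.** A reader might infer that the false-positive rate is certainly far above 5%. Step 4 depends on assumed source sizes, and with a very large source the inflation is negligible. Totals over both tails would also mix false 'lower' with false 'increase' results; the second is the error that bears on the hypothesis.
- **Only results near the cut-off are at risk.** At the stated target of 2%, 'increase' is declared against 1% with over 99.9% probability at n = 5000. The 0.7% to 1.0% case is a smaller effect than item 9 set out to detect.
- **The documents do not show that the 1% is out of date.** The Background remark that the "frequency of DVT following TKA is decreasing over time" concerns TKA patients on warfarin, not symptomatic VTE on 35 days of LMWH. The local fast-track rates are not 35-day LMWH rates either.
- **A two-sample comparison is not a full cure.** It adds the baseline's sampling error but does not correct drift.

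**Conclusion.** The concern holds in conditional form. If item 9's test is used to conclude 'no increase' over 35 days of LMWH, the conclusion rests on an unsourced 1% treated as exact. With 5000 patients and no treatment effect, a true 35-day risk 0.1 to 0.3 points above 1% raises the false 'increase' rate from 2.3% to between 10% and 52%. A true risk of 0.7% leaves a rise to 1.0% almost undetected (about 2%). These figures need only the exact binomial rule and the stated true risks. The 16%, 10% and 6% for sources of 2000, 4000 and 10,000 patients illustrate the effect under sizes that the documents do not give.

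The documents do not support saying that alpha fails against 1%, that the 1% is known to be wrong, or that large effects would be missed. The change is advisable because it is nearly free and alters what the study may claim about results near 1.3%.

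**What to change.** In Section 4 as changed by Section 19, item 9:

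1. Report the 90-day symptomatic VTE rate with its exact CI.
2. Add a tipping-point table that repeats the conclusion for 35-day baselines from 0.5% to 1.5%. This is the part that addresses drift as well as imprecision. With 5000 patients, the event count for 'increase' moves from 36 (baseline 0.5%) through 65 (1.0%) to 93 (1.5%).
3. State the events, patients and follow-up window behind the 1%.
4. Where those counts exist, also give the difference in proportions with a CI that includes the baseline's sampling error, noting that this does not correct drift.
5. Where they do not exist, call 1% a fixed performance goal and do not describe the result as no increase versus 35 days of LMWH.

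The cost is one table, some wording and a more cautious conclusion near the cut-off. No new cohort data are needed. The two-sample interval in item 4 is wider: approximate power for 1% versus 2% with 5000 patients is 60%, 86% or 99.7% if the source has 1000, 2000 or 10,000 patients. It should therefore supplement the exact CI and the table, not replace them.
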